9. PHARMACOKINETIC ANALYSES

The pharmacokinetic (PK) analyses will be based on the Pharmacokinetic population, unless otherwise specified.

Pharmacokinetic data from Part 1 of the study will be analyzed using standard non-compartmental methods, and combined data from Part 1 and Part 2 of the study will be analyzed in a population approach using nonlinear mixed effects modeling. Full details are presented in [Appendix 12](#): List of Data Displays.

9.1. Endpoint / Variables

9.1.1. Drug Concentration Measures

Refer to [Appendix 5](#): Data Display Standards & Handling Conventions (Section 16.5.3 Reporting Standards for Pharmacokinetic)

9.1.2. Derived Pharmacokinetic Parameters

9.1.2.1. Non-compartmental Analysis

- The pharmacokinetic parameters for Part 1 will be calculated by standard non-compartmental analysis according to current working practices and using Phoenix WinNonlin, version 6.3 or later.
- All calculations of non-compartmental parameters will be based on actual sampling times.
- Pharmacokinetic parameters described in [Table 7](#) will be determined from the Cycle 1 plasma concentration-time data in Part 1 of the study separately for each analyte, as data permit.

Table 7 Derived Pharmacokinetic Parameters

Parameter	Parameter Description
AUC(0-t)	Area under the concentration-time curve from time zero to the time of the last quantifiable concentration (C(t)) will be calculated using the linear trapezoidal rule for each incremental trapezoid and the log trapezoidal rule for each decremental trapezoid.
AUC(0- τ)	Area under the concentration-time curve during the dosing interval
AUC(0- ∞)	Area under the concentration-time curve extrapolated to infinity will be calculated as: AUC = AUC(0-t) + C(t) / lambda_z
%AUC _{ex}	The percentage of AUC (0- ∞) obtained by extrapolation (%AUC _{ex}) will be calculated as: [AUC(0-inf) – AUC(0-t)] / AUC(0-inf) x 100
C _{max}	Maximum observed concentration, determined directly from the concentration-time data for each cycle. For cys-mcMMAF, C _{max} will not be derived when only predose and EOI samples were collected.
t _{max}	Time to reach C _{max} , determined directly from the concentration-time data for each cycle
C _{τ}	Trough concentration prior to the next dose for each cycle

Parameter	Parameter Description
Ctrough	
$t_{1/2}$	Apparent terminal half-life will be calculated as: $t_{1/2} = \ln 2 / \lambda_{z}$
tlast	Time of last observed quantifiable concentration
CL	Clearance
Vss	Volume of distribution at steady state
λ_z , λ_{z}	Terminal phase rate constant
Ae(0-t)	Urinary recovery of cys-mcMMAF within t hours after start of infusion will be calculated as: $\text{Urine cys-mcMMAF concentration} \times 24\text{-h urine volume}$ t = time from start of infusion to end of urine collection period (≤ 24 h)
Fe(0-t)	Fraction of cys-mcMMAF dose excreted within t hours after start of infusion will be calculated as: $Ae(0-t) / \text{cys-mcMMAF dose}$

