
 Urinary recovery of unchanged cys-mcMMAF within the 24 h period collection (Ae(0-24)) will be calculated. Fraction of total cys-mcMMAF dose excreted (Fe) in the 24-h interval will be 	
 Urinary recovery of unchanged cys-mcMMAF within t hours after the start of infusion (Ae(0-t)) will be calculated. Fraction of total cys-mcMMAF dose 	
 The 24-h urine collection period may start at a time other than the start of infusion; therefore, the urine collection period may not be 24 h from the start of

Protocol	Reporting & Analysis Plan	
Statistical Analysis Plan	Statistical Analysis Plan	Rationale for Changes

estimated as $Ae(0-24)/cys-mcMMAF$ Dose
	
excreted within t hours after the start of infusion ($Fe(0-t)$) will be estimated as $Ae(0-t)/cys-mcMMAF$ dose. Time t is the time from the start of the infusion to the end of the urine collection period (≤ 24 h)..
	
infusion, and the pharmacokinetic parameter definitions have been changed to reflect this.

 • Not included 	
 • Calculation of analyte ratios as CEOI (total mAb, unbound mAb, or cys-mcMMAF) to CEOI (ADC) or Ctough (total mAb, unbound mAb, or cys-mcMMAF) to Ctough (ADC) at each cycle at which they are determined, adjusted for molecular weights 	
 • To assess exposures to each compound relative to ADC at EOI and trough for each cycle

 • Descriptive statistics (mean, standard deviation, median, range) will be used to summarize observed laboratory values and change from baseline in observed value at each scheduled visit, as appropriate 	
 • Descriptive statistics (mean, standard deviation, median, range) will be used to summarize change from baseline in observed value at each scheduled visit, as appropriate 	
 • To be consistent with the latest GSK (IDSL) standard.

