Serum (cytokines/chemokines)		X ¹⁹	X			X ¹⁹	At predose and EOI on D1 of each cycle	X	
Serum (anti-drug-antibodies)	X					X ²⁰	At the start of cycles 3 ²⁰ , 6 ²⁰ , 9 ²⁰ , 12 ²⁰ and 16 ²⁰	X	
Plasma-cfDNA	X							X	
Peripheral blood (flow for TBNK)	X ¹⁵					X ¹⁵	At the start of each cycle ¹⁵	X ¹⁵	
Serial Pharmacokinetics (blood)		X ²¹	X ²¹	X ²¹	X ²¹	X ²¹	C3D1 only ²¹	X ²²	
Urine PK	X ²³					X ²³	Day 1 of cycles 4 ²³ , 7 ²³ , 10 ²³ , 13 ²³ , 16 ²³		
Premedication if needed		X				X	At the start of each cycle		
GSK2857916 administration		X ²⁴				X ²⁴	X ²⁴		
Steroid eye drops		X ²⁵				X ²⁵	X ²⁵		
Adverse Events							Continuous		

Time and Events Table for Full Study (Cycle = 21 days)									
Study Assessments ¹	Screen ²	Day 1 C1	Day 2 C1	Day 8 C1	Day 15 C1	Day 1 C2	D1 of C3-C16	End of Study Treatment	3-Month Off-study Follow-up
Concomitant Medications	X	Continuous							
Survival Status									X ²⁶
Subsequent Treatment									X ²⁶

- Assessments scheduled on days of dosing should be done prior to drug administration, unless otherwise specified. All other assessments can be ± 3 days of scheduled occurrence unless otherwise specified.
- All Screening assessments must be performed within 14 days prior to first dose unless otherwise specified. Informed Consent must be signed before any study-specific assessments are performed.
- Screening examination to include BCVA (best-corrected visual acuity), slit lamp examination (with special focus on cornea), intraocular pressure, and dilated fundoscopic examination may be performed within 21 days prior to first dose.
- On-study exams to include BCVA (best-corrected visual acuity) and slit lamp examination (with special focus on cornea); window for exams is up to 3 days prior to dosing.
- On initial (first infusion) dosing day, vital signs must be assessed at pre-dose (within 30 minutes prior to SOI), +10 minutes and +30 minutes (±5 min) after SOI, EOI, and 1 hour post EOI. On subsequent dosing days, vital signs must be assessed at pre-dose (within 30 minutes prior to SOI), +30 minutes after SOI, and EOI. The Sentinel Subject must be observed for at least 24 hours post EOI. **On days where vital sign timepoints align with PK sampling timepoints, vital signs should be assessed prior to PK samples being drawn.**
- If completed within 72 hrs prior to the first dose, this assessment need not be repeated on Day 1 of Cycle 1. Refer to Table 15 of the protocol for comprehensive list of lab tests.

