19. Collect cytokines at predose (within 30 minutes prior to SOI) and EOI (± 5 min) (even when infusion is interrupted or halted) to assess allergic reaction)
20. All ADA samples will be collected prior to each infusion
21. PK samples to be taken (in all subjects) for both GSK2857916 and cys-mcMMAF measurement: C1D1 at pre-dose (within 30 minutes prior to SOI), 0.5 h after the start of the infusion (SOI) (± 5 min), at the end of infusion (EOI) just before EOI, 1 h after EOI, 3 h after EOI (± 5 min), 8 h after EOI (± 15 min), 24h after EOI (± 1 h) (Day 2); C1D8 1 sample; C1D15 1 sample; C2D1, at pre-dose (within 30 minutes prior to SOI) and at the EOI (just before EOI); C3D1 at pre-dose (within 30 minutes prior to SOI) and at the EOI (just before EOI).
22. Collect 1 PK sample at each subject's final visit.
23. Pre-specified amounts of urine will be collected for PK analysis from the 24 hour urine collection at Screening, C2D1, C4D1, C7D1, C10D1, C13D1, and C16D1. Refer to Section 7.4.2 of the protocol for details.
24. Study drug administration ± 3 day window only
25. Prophylaxis with prednisolone phosphate 1% or dexamethasone 0.1% 1 drop QID x 4 days starting 1 day prior to treatment
26. Record subject's survival status and whether subsequent treatment for disease was given. Subject does not need to come in for visit.

Abbreviations:

ADA = Antibody Drug Antibody; ALP = alkaline phosphatase; BCVA = best corrected visual acuity; BNP = B-type natriuretic peptide; C1D1 = Cycle 1 Day 1, etc.; cfDNA = Circulating free DNA; CK = creatinine kinase; CRP = C-reactive protein; EM = extramedullary; EOI = End of Infusion; FLC = free light chain; PD = Pharmacodynamics; PK = Pharmacokinetics; QID = 4 times a day; SOI = start of infusion; SPEP = serum protein electrophoresis; UPEP = urine protein electrophoresis

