4.0063	PK	PK06	Summary of Derived GSK2857916 (Total Antibody) PK Parameters (Part 2 NHL)	PK06 with both transformed and untransformed values.	SAC
4.0070	PK	PK06	Summary of Derived GSK2857916 (Unbound Antibody) PK Parameters (Part 1)	By dose level PK06 with both transformed and untransformed values.	SAC [A]
4.0071	PK	PK06	Summary of Derived GSK2857916 (Unbound Antibody) PK Parameters (Part 2 MM)	PK06 with both transformed and untransformed values. If data was not collected, present "No data to	SAC [A]

CONFIDENTIAL

BMA117159

Pharmacokinetic: Tables					
No.	Population	IDSL / Example Shell	Title	Programming Notes	Deliverable [Priority]
				report"	
4.0073	PK	PK06	Summary of Derived GSK2857916 (Unbound Antibody) PK Parameters (Part 2 NHL)	PK06 with both transformed and untransformed values. If data was not collected, present "No data to report"	SAC
4.0080	PK	PK06	Summary of Derived cys-mcMMAF PK Parameter (Part 1)	By dose level PK06 with both transformed and untransformed values.	SAC [A]
4.0081	PK	PK06	Summary of Derived cys-mcMMAF PK Parameter (Part 2 MM)	PK06 with both transformed and untransformed values.	SAC [A]
4.0083	PK	PK06	Summary of Derived cys-mcMMAF PK Parameter (Part 2 NHL)	PK06 with both transformed and untransformed values.	SAC
4.0090	PK	PK13	Listing of Derived GSK2857916 (ADC) PK Parameters (Untransformed) (MM)		SAC [A]
4.0091	PK	PK13	Listing of Derived GSK2857916 (ADC) PK Parameters (Untransformed) (NHL)		SAC
4.0100	PK	PK13	Listing of Derived GSK2857916 (Total Antibody) PK Parameters (Untransformed) (MM)		SAC [A]
4.0101	PK	PK13	Listing of Derived GSK2857916 (Total Antibody) PK Parameters (Untransformed) (NHL)		SAC
4.0110	PK	PK13	Listing of Derived GSK2857916 (Unbound Antibody) PK Parameters (Untransformed) (MM)		SAC [A]
4.0111	PK	PK13	Listing of Derived GSK2857916 (Unbound Antibody) PK Parameters (Untransformed) (NHL)		SAC
4.0120	PK	PK13	Listing of Derived cys-mcMMAF PK Parameters		SAC [A]

Pharmacokinetic: Tables					
No.	Population	IDSL / Example Shell	Title	Programming Notes	Deliverable [Priority]
			(Untransformed) (MM)		
4.0121	PK	PK13	Listing of Derived cys-mcMMAF PK Parameters (Untransformed) (NHL)		SAC
4.0130	PK	PK03	Summary of cys-mcMMAF Pharmacokinetic Urine Excretion Data (Part 1)		SAC [A]
4.0140	PK	PK11	Listing of cys-mcMMAF Urine Excretion Data (Part 1)	replace Amount Excreted and Excretion Rate with Ae(0-24) and Fe	SAC [A]

Pharmacokinetic: Tables					

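### Ae(0-t) for cys-mcMMAF is labelled as post-infusion recovery but computed from the whole 24-h urine collection, so drug left from an earlier dose can inflate Ae and Fe

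*SAP*

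**What the plan says.** Section 9.1.2.1, Table 7, introduces the parameter with "Urinary recovery of cys-mcMMAF within t hours after start of infusion will be calculated as" and gives the product of "Urine cys-mcMMAF concentration" and the 24-h urine volume. It adds "t = time from start of infusion to end of urine collection period", capped at 24 h. Fe(0-t) is that amount divided by the cys-mcMMAF dose.

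Section 2.1 explains why Ae(0-24) became Ae(0-t): "The 24-h urine collection period may start at a time other than the start of infusion". It repeats the definition: "Time t is the time from the start of the infusion to the end of the urine collection period", again at most 24 h.

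The Part 1 schedule in section 16.2.2.1, footnote 23, says "Pre-specified amounts of urine will be collected for PK analysis from the 24 hour urine collection at Screening, C2D1, C4D1" and at later cycles (C7D1, C10D1, C13D1, C16D1). It lists no collection at C1D1 and refers to protocol section 7.4.2 for details.

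In section 16.12.10, the programming note for listing 4.0140 still reads "replace Amount Excreted and Excretion Rate with Ae(0-24) and Fe".

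**The concern.** The amendment changed the name of the parameter and the meaning of t, but not the calculation. A 24-h collection that ends no more than 24 h after the infusion starts must begin at or before the infusion. If it begins before, the label covers 0 to t while the formula covers the full 24 h. No step splits, subtracts or excludes the pre-infusion part.

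This matters because every on-treatment urine sample follows at least one earlier dose. Any cys-mcMMAF still being excreted before the infusion is counted as recovery after it and divided by the new dose. The error would vary between subjects with the timing of their collections. Ae and Fe are the only urinary recovery parameters in the SAP, so no other urine result would show the problem.

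**Working it through.** The SAP states no numerical Ae or Fe, so there is no figure to reproduce. The check is a mass balance.

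**Inputs**
- Formula: concentration × 24-h volume (section 9.1.2.1, Table 7).
- t: infusion start to end of collection, at most 24 h (Table 7 and section 2.1).
- The concentration is measured on urine taken from that same 24-h collection (section 16.2.2.1, footnote 23).
- On-treatment collections: C2D1 or later (same footnote).
- r, the mean hourly excretion before the infusion divided by the mean hourly excretion in 0-t: not in the documents. It is an assumption, shown from 0 to 1.
- The collection is taken to last a full 24 h, as its name says.

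**Step 1: what the formula returns.** Pooled concentration × pooled volume = A_pre + A_post, the correct total for the collection. The quantity defined as Ae(0-t) is A_post alone.

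**Step 2: the ratio.** Let e be the hourly rate in 0-t. Then A_post = e·t and A_pre = r·e·(24 - t), so

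plan's Ae / defined Ae(0-t) = 1 + r(24 - t)/t.

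Fe carries the same factor because it is Ae divided by a fixed dose.

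**Step 3: numbers.** The multiplier (24 - t)/t is 18/6 = 3 at 6 h, 12/12 = 1 at 12 h, 6/18 = 0.333 at 18 h, and 0 at 24 h.

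| r | t = 6 h | t = 12 h | t = 18 h | t = 24 h |
|---|---|---|---|---|
| 0 | 1.00 | 1.00 | 1.00 | 1.00 |
| 0.1 | 1.30 | 1.10 | 1.03 | 1.00 |
| 0.5 | 2.50 | 1.50 | 1.17 | 1.00 |
| 1 | 4.00 | 2.00 | 1.33 | 1.00 |

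**Step 4: why prorating the volume is not a repair.** Suppose 1000 mL of drug-free urine is passed before the infusion, and 1000 mL containing 10 µg after it, with t = 12 h. The pooled concentration is 10/2000 = 0.005 µg/mL. The plan's formula gives 0.005 × 2000 = 10 µg, which is right. Scaling the volume by t/24 gives 0.005 × 1000 = 5 µg, half the true amount. With drug-free pre-infusion urine, prorating returns 0.25, 0.50 and 0.75 of the truth at t = 6, 12 and 18 h.

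**The case against.** The strongest reply is that using the whole volume is not in itself an error. Drug-free pre-infusion urine dilutes the pooled concentration by exactly the volume it adds, so the total is unchanged. That is correct. A reader might infer that Fe is overstated whenever t is below 24 h, but the documents do not support this. The excess is only the drug actually present in pre-infusion urine, and no residual level is given. Appendix 9 puts the Cycle 2 pre-dose sample at a nominal 504 h, three weeks after the previous dose, so r may be small or nil. Against that, section 9.3.1.2 plans trough-based accumulation ratios for cys-mcMMAF, so measurable residue is contemplated. It also notes that the peak is mostly not at or near the end of infusion, so early post-infusion excretion need not dwarf any carry-over. Neither point fixes r.

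A reader might also infer that some collections finish before dosing and give an Fe for a dose not yet received, since footnote 1 of section 16.2.2.1 says "Assessments scheduled on days of dosing should be done prior to drug administration, unless otherwise specified". This cannot be established. That default yields to other instructions, and footnote 23 sends the collection details to a protocol section not available here. Table 7 parameters are also derived only as data permit.

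Two further points stand. Restricting Fe to collections that start at the infusion does not remove carry-over excreted after it. And the output is minor: section 2.2 does not name urinary recovery among its example PK parameters, and it feeds one Part 1 summary (4.0130) and one Part 1 listing (4.0140), with no decision rule attached.

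**Conclusion.** The point holds as a mismatch between label and formula, with a possible upward bias. Ae(0-t) is defined over the time from infusion start to the end of collection but computed over the full 24 h. The two agree only if t = 24 h or the earlier urine contains no drug. Otherwise Ae and Fe are too high by 1 + r(24 - t)/t. Over r from 0 to 1 this runs from 1.00 to 1.33 at t = 18 h, to 2.00 at 12 h and to 4.00 at 6 h. The direction is certain given a full 24-h collection and t of at most 24 h; the size is unknown, because the SAP gives neither r nor the distribution of t.

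Listing 4.0140 still asks for the superseded Ae(0-24), whatever r is. Severity is low: this is a descriptive Part 1 result.

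**What to change.** In Table 7, define the measured quantity as Ae(t1-t2) = concentration × volume, with t1 and t2 the actual start and end of collection relative to infusion start. Derive Ae(0-t) and Fe(0-t) only for collections that start at the infusion within a tolerance stated in advance. List all other collections as Ae(t1-t2) without an Fe. Do not prorate the volume by t/24.

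Add a sentence that an Fe from Cycle 2 onward may still include carry-over from an earlier dose excreted after the infusion. Change the note for listing 4.0140 from Ae(0-24) to the same definition.

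The cost is SAP wording and a derivation filter on recorded collection times. The drawback is that fewer subjects contribute an Fe.

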9.2. Population of Interest

The primary pharmacokinetic analyses will be based on the “Pharmacokinetic” population, unless otherwise specified.

9.3. Statistical Analyses / Methods

Details of the planned displays are provided in [Appendix 12: List of Data Displays](#) and will be based on GSK Data Standards and statistical principles. Unless otherwise specified, endpoints / variables defined in Section 9.1 will be summarised using descriptive statistics, graphically presented (where appropriate) and listed.

9.3.1. Statistical Methodology Specification

The following pharmacokinetic statistical analyses will only be performed if sufficient data are available.

9.3.1.1. Exploratory assessment of dose proportionality:

The PK-dose relationship initially will be examined graphically by plotting $AUC(0-\infty)$, $AUC(0-\tau)$, and C_{max} as a function of the dose levels administered; $AUC(0-t)$ may be used for cys-mcMMAF. Plots of PK parameters versus dose will be produced, with two plots for each PK parameter. The first will be on a linear scale, and the second will use the logarithmic scale for both axes.

In practice, at least three dose levels are required to assess dose proportionality. Hence, if more than two dose cohorts are required to reach MTD (or recommended dose based on available safety, PK, and response data), dose proportionality of GSK2857916, unbound

antibody, total antibody, and cys-mcMMAF following administration in Cycle 1 will be evaluated, if data permit, using the power model.

Dose Proportionality Analysis
Endpoint(s)

 • Log_e-transformed single dose PK parameters listed below for each analyte will be investigated for Cycle 1 Day 1 in Part 1 if data permit. 
 ○ AUC(0-∞) or AUC(0-τ), Cmax, Ctrough for GSK2857916 (ADC), total antibody, unbound antibody ○ AUC(0-t), Cmax, Ctrough for cys-mcMMAF
Model Specification

 • Endpoints for each analyte will be separately analyzed using appropriate methods for GSK2857916 doses. • Power Model 
 • Dose proportionality of PK parameters defined above in Endpoints will be assessed following single dose administration of GSK2857916 between 0.03 mg/kg and 4.6 mg/kg, using the power model as described below: $y = \alpha * \text{dose}^\beta$ 
where y denotes the PK parameter being analyzed and α depends on subject.
 • Dose proportionality implies that β=1 and will be assessed by estimating β along with its 90% confidence interval. The exponent, β, in the power model will be estimated by regressing the log_e-transformed PK parameter on log_e-transformed dose. • The power model will be fitted by restricted maximum likelihood (REML) using SAS Proc Mixed. A power model with only subject as a random effect power model will be fitted. The mean slope will be estimated from the power model and the corresponding 90% confidence interval calculated. Model specification (e.g. random statement, variance structure) could be explored for achieving convergence. • If the 90% confidence interval for the slope regressing dose against exposure is contained within the interval (0.8, 1.25), the exposure will be considered to be dose proportional.
Model Checking & Diagnostics

 • Refer to Section 9.3.2.
Model Results Presentation

 • Power Model 
 • The mean slope and the corresponding 90% confidence interval for each parameter will be produced in tabular format. • Comparative plots of individual PK parameters will be generated by treatment on linear and semi-logarithmic scales. • Supportive SAS output from statistical analysis will be generated.

9.3.1.2. Assessment of Accumulation Ratio:

To assess the extent of accumulation following GSK2857916 repeat dosing, the observed accumulation ratio (Ro) for GSK2857916, total antibody, unbound antibody, and cys-mcMMAF will be determined as ratio of concentration at end of infusion (CEOI) and

Ctrough at steady-state to CEOI and Ctrough after the first dose, respectively, adjusted for any change in GSK2857916 dose.

For the purpose of accumulation ratio analysis, CEOI at each cycle will be used. Preliminary analysis found that cys-mcMMAF Cmax did not occur at or near EOI in most cases; therefore, the cys-mcMMAF accumulation ratio based on CEOI is not based on Cmax.

Accumulation ration will only be derived and analyses will only be performed for subjects who received at least 80% of the planned dose at cycle 1. $Ro(CEOI) = CEOI_{Cx D1} / CEOI_{C1 D1}$;
 $x = 3, 5$;

$Ro(Ctrough) = Ctrough_{Cx D1} / Ctrough_{C1 D1}$;
 $x = 4$;

Only one accumulation ratio for CEOI and Ctrough will be derived for each subject according to the rules below:

Preliminary pharmacokinetic data indicate that the pharmacokinetics for the third consecutive dose given at the planned interval will be at steady state. Therefore, based on the study design, subjects who meet one of the following criteria will be at steady state

When assessing accumulation ratio based on CEOI:

- Subjects who receive the same dose without delay or change for Cycles 1, 2, and 3 (i.e., with dosing delays of ≤ 3 days). In this case, Cycle 3 represents steady state. Accumulation ratios are calculated as Cycle 3/Cycle 1.
- Subjects who have a dose reduction or two by Cycle 3, but then dose is maintained at the same level and interval through Cycle 5. Cycle 5 represents steady-state pharmacokinetics, but dose adjustment is needed. Dose adjustment: multiply CEOI values by the ratio (starting dose level/Cycle 3-5 dose level). Accumulation ratio = adjusted Cycle 5/Cycle 1.

When assessing accumulation ratio based on Ctrough:

- Subjects who receive the same dose without delay or change to Cycle 4 (i.e., with dosing delays of ≤ 3 days). Accumulation ratio = Cycle 4 Ctrough/Cycle 1 Ctrough.
- Subjects who have a dose reduction by Cycle 2, but then dose is maintained at the same level and interval through Cycle 4. Cycle 4 represents steady-state pharmacokinetics, but dose adjustment is needed. Dose adjustment: multiply Ctrough values by the ratio (starting dose level/Cycle 2-4 dose level). Accumulation ratio = adjusted Cycle 4 Ctrough/Cycle 1 Ctrough.

Accumulation ratios of CEOI and Ctrough will be summarised using descriptive statistics by planned initial dose level, graphically presented (where appropriate) and listed.

9.3.1.3. Assessment of Analyte Ratios:

For the purpose of analyte ratio analysis, CEOI at each cycle will be used, and Ctrough is defined as the concentration immediately prior to the next cycle dose. Preliminary analysis found that cys-mcMMAF Cmax did not occur at or near EOI in most cases; therefore, the cys-mcMMAF analyte ratio based on EOI is not based on Cmax.

Analyte Ratios of CEOI and Ctrough are defined as the ratio of CEOI and Ctrough for analytes: unbound antibody, total antibody, and cys-mcMMAF to CEOI and Ctrough for analyte ADC at each cycle:

Ratio of analytes at each cycle versus ADC at Cycle X:

$$Ra \text{ (CEOI)} = \frac{\text{CEOI (unbound antibody, total antibody, cys-mcMMAF) Cycle X}}{\text{CEOI (ADC) Cycle X}}$$

X = 1, 2, 3, 5;

$$Ra \text{ (Ctrough)} = \frac{\text{Ctrough (unbound antibody, total antibody, cys-mcMMAF) Cycle X}}{\text{Ctrough (ADC) Cycle X}}$$

X = 1, 2, 4;

To fit into the analysis model, the units of the analytes need to be converted from ng/mL or pg/mL to nM as below.

	Original unit	Operation	Converted unit
ADC	ng/mL	/152.1	nM
Total Antibody	ng/mL	/152.1	nM
Unbound Antibody	ng/mL	/152.1	nM
cys-mcMMAF	pg/mL	/1045	nM

Analyte ratios of CEOI and Ctrough for each will be summarised using descriptive statistics by planned initial dose level and cycle, graphically presented (where appropriate) and listed.

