5. CONSIDERATIONS FOR DATA ANALYSES AND DATA HANDLING CONVENTIONS

5.1. Study Treatment & Sub-group Display Descriptors

Treatment Group Descriptions				
RandAll NG		Data Displays for Reporting		
Code	Description ^[1]	Description ^[2]	Data Display	Order in TLF
A	Active Treatment	GSK2857916 0.03 mg/kg (Part 1 MM)	0.03 mg/kg	1
		GSK2857916 0.06 mg/kg (Part 1 MM)	0.06 mg/kg	2
		GSK2857916 0.12 mg/kg (Part 1 MM)	0.12 mg/kg	3
		GSK2857916 0.24 mg/kg (Part 1 MM)	0.24 mg/kg	4
		GSK2857916 0.48 mg/kg (Part 1 MM)	0.48 mg/kg	5
		GSK2857916 0.96 mg/kg (Part 1 MM)	0.96 mg/kg	6
		GSK2857916 1.92 mg/kg (Part 1 MM)	1.92 mg/kg	7
		GSK2857916 2.50 mg/kg (Part 1 MM)	2.50 mg/kg	8
		GSK2857916 3.40 mg/kg (Part 1 MM)	3.40 mg/kg	9
		GSK2857916 4.60 mg/kg (Part 1 MM)	4.60 mg/kg	10
		GSK2857916 3.40 mg/kg (Part 2 MM)	3.40 MM	11
		GSK2857916 3.40 mg/kg (Part 2 NHL)	3.40 NHL	12

Notes:

^[1] This is a single-arm study and only active treatment is planned for the study.

^[2] Part 1: dose escalation phase; Part 2: Expansion Cohort; MM: multiple myeloma; NHL: Lymphoma.

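### The dose-proportionality rule puts exposure-ratio limits (0.8, 1.25) on the power-model exponent, so over the 153-fold dose range clearly non-proportional exposure can still be labelled proportional

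*SAP*

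**What the plan says.** Section 9.3.1.1 models each PK parameter as y = α·dose^β, fitted on the log–log scale, for "single dose administration of GSK2857916 between 0.03 mg/kg and 4.6 mg/kg". These end doses match the lowest and highest Part 1 levels in Section 5.1.

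The criterion has two steps. First, "Dose proportionality implies that β=1 and will be assessed by estimating β along with its 90% confidence interval". Second, if that interval is "contained within the interval (0.8, 1.25), the exposure will be considered to be dose proportional". The limits therefore apply to the exponent. Nothing ties them to the width of the dose range, and the section sets no limit on the exposure ratio itself.

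The rule covers AUC, Cmax and Ctrough for the ADC, total antibody, unbound antibody and cys-mcMMAF, and the results go into Table 4.0150 (Section 16.12.10). The heading is "Exploratory assessment of dose proportionality", and Section 9.3.1 makes the analysis conditional on sufficient data.

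**The concern.** The pair 0.8 and 1.25 are reciprocals, which makes them symmetric for a ratio. On an exponent they sit unevenly about 1 (0.20 below, 0.25 above), and their meaning depends on how far the doses spread. Under the plan's own model, dose-normalised exposure varies as dose^(β−1). A slope limit that is tight over a two- or three-fold range becomes loose over a hundred-fold range.

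At stake is the wording of a PK conclusion. A report that follows the plan could state that exposure is dose proportional from 0.03 to 4.6 mg/kg when the fitted model itself shows a material departure over that range.

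**Working it through.** The SAP gives no power, sample size or variance for this analysis, so there is no stated figure to reproduce.

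**1. What the slope limits mean (inputs from the SAP only).** Doses 0.03 and 4.6 mg/kg (Sections 9.3.1.1 and 5.1); slope limits 0.8 and 1.25.

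- r = 4.6/0.03 = 153.3; ln r = 5.033
- Ratio of dose-normalised exposure, highest to lowest dose: r^(β−1)
- β = 0.80: 153.3^(−0.20) = 0.365, a 63% fall
- β = 1.25: 153.3^(0.25) = 3.52, a rise to about 3.5 times

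**2. The same limits over narrower ranges of planned Part 1 doses.**

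| Range (mg/kg) | r | Ratio at β = 0.8 | Ratio at β = 1.25 |
|---|---|---|---|
| 0.03–4.6 | 153.3 | 0.37 | 3.52 |
| 0.24–4.6 | 19.2 | 0.55 | 2.09 |
| 0.48–4.6 | 9.6 | 0.64 | 1.76 |
| 0.96–4.6 | 4.8 | 0.73 | 1.48 |
| 1.92–4.6 | 2.4 | 0.84 | 1.24 |

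**3. Slope limits that would hold the ratio within 0.8–1.25.** 1 ± ln(1.25)/ln(r) = 1 ± 0.2231/5.033, which is 0.956 to 1.044. A looser target of 0.5–2.0 gives 0.862 to 1.138, still narrower than the plan's limits. Slope limits of 0.8 and 1.25 correspond to exposure ratios of 0.8 and 1.25 only at r = 3.05 (lower limit) and r = 2.44 (upper limit).

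**4. How often a non-proportional slope would pass (assumed layout and SD).** The SAP gives neither cohort sizes nor PK variability. Assume one subject at each of 0.03, 0.06, 0.12 and 0.24, four each at 0.48, 0.96 and 1.92, eight at 2.5, three at 3.4 and six at 4.6 (n = 33), with log-scale SD 0.25, 0.35 or 0.50.

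- The sum of squares of log dose about its mean is 52.9. SE = SD/√52.9 = 0.034, 0.048, 0.069.
- 90% CI half-width = 1.696 × SE (t, 31 df) = 0.058, 0.082, 0.117.
- True slope 1.10 means 153.3^0.10 = 1.65, or 65% over-proportional across the range. At SD 0.35 the estimate must fall below 1.25 − 0.082 = 1.168; (1.168 − 1.10)/0.048 ≈ 1.42, so it passes 92% of the time. For SD 0.25 and 0.50: 100% and 68%.
- True slope 0.90 means 153.3^(−0.10) = 0.60, or 40% under. It passes 65% of the time at SD 0.35; 89% and 40% at SD 0.25 and 0.50.
- With a smaller layout (one at each of the four lowest doses, three at each other level, n = 22) and SD 0.35: sum of squares 43.6, SE 0.053, half-width 1.725 × 0.053 = 0.091. The pass rates are 87% and 56%.

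**5. Whether range-scaled limits could be met.** In the 33-subject layout the half-widths of 0.058 to 0.117 all exceed the margin of 0.044. Refitting on 0.96–4.6 mg/kg (25 subjects, sum of squares 6.45) gives half-widths of 0.169 to 0.337 against a margin of 0.2231/1.567 = 0.142. With the SD at its assumed value, neither range passes even when the true slope is exactly 1.00.

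**The case against.** The strongest reply is about consequence. The Part 2 dose is 3.4 mg/kg, and over the surrounding Part 1 levels (1.92–4.6 mg/kg) the plan's limits imply 0.84–1.24, which is what a 0.8–1.25 criterion intends. The large departures appear only when 4.6 is compared with 0.03 mg/kg. The slope and its 90% CI are tabulated in any case, so a careful reader can judge the departure. This all stands.

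A reader might infer that the rule threatens dose–exposure extrapolation around the recommended dose. The SAP does not support that. No section uses the label for extrapolation; the exposure–response datasets take individual clearances and predicted concentrations from the population PK model (Section 16.10.1); and escalation rests on the N-CRM and all available data (Section 3.1.1).

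A reader might also infer that a 3.5-fold departure would itself pass. It would not: the whole CI must lie inside, so 0.37 and 3.52 are bounds that a passing estimate cannot reach. The pass rates also rest on an assumed layout and SD.

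Finally, range-scaled limits may look unhelpful because they cannot be met at this size. That bears on the form of the fix. It does not make the present limits right for the stated range.

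**Conclusion.** The rule is wrong as written for the range it names. Its limits correspond to dose-normalised ratios of 0.37 and 3.52 over 0.03–4.6 mg/kg. This follows from the plan's own model and doses and needs no assumption. Under the assumed 33-subject layout, a slope that is 65% over-proportional across the range would be called proportional in 68% to 100% of cases for SD 0.50 to 0.25.

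If low-dose parameters cannot be estimated, the problem shrinks with the range: 0.64–1.76 remains over 0.48–4.6 mg/kg, and it nearly vanishes over 1.92–4.6 mg/kg. The harm is limited to a mislabelled exploratory PK conclusion. This is a point to consider, not one on which the trial's decisions turn.

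**What to change.** Remove the fixed (0.8, 1.25) slope rule from Section 9.3.1.1. For each parameter and analyte report:

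- the slope b and its 90% CI (already planned);
- the implied dose-normalised ratio r^(b−1) and its 90% CI, with r the ratio of highest to lowest dose actually analysed;
- the largest dose ratio over which the CI supports an exposure ratio within 0.8–1.25. This is the smaller of exp[ln(0.8)/(b_L − 1)] when b_L < 1 and exp[ln(1.25)/(b_U − 1)] when b_U > 1, where b_L and b_U are the CI limits.

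For example, an estimate of exactly 1.00 with half-width 0.0816 (SD 0.35 in the assumed layout) would support proportionality over exp(0.2231/0.0816) ≈ 15-fold. That is informative even though the full range is not covered.

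If a label is kept, use limits of 1 + ln(0.8)/ln(r) to 1 + ln(1.25)/ln(r): proportional if the CI lies inside, not proportional if it lies wholly outside, inconclusive otherwise.

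The cost is SAP wording and added columns in Table 4.0150, with no new data and no change of model. The downside should be stated openly: on the assumptions above, the full-range label would come out as inconclusive or not proportional, never as proportional, and restricting the fit to 0.96–4.6 mg/kg would not change that.
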